APPENDIX G. GUIDANCE IN CASE OF INCREASE IN ALT OR AST

1. If ALT or AST > 3x ULN and Total Bilirubin < 2x ULN:

- The event must be reported to the Sponsor within 24 hours.
- The following laboratory tests will be performed: alkaline phosphatase, total and conjugated bilirubin, prothrombin time, international normalized ratio (INR), creatinine phosphokinase (CPK), serum creatinine, complete blood count, hepatitis A virus (HAV), hepatitis B virus (HBV), hepatitis C virus (HCV), hepatitis D virus (HDV), and hepatitis E virus (HEV).
- Recent medical history will be investigated specifically for intercurrent illness, malaise with or without loss of consciousness, dizziness, hypotension, episodes of arrhythmia, and muscular injury.
- Concomitant medications, including recreational drugs, nonprescription medications and herbal and dietary supplement preparations, will be reviewed and any substance potentially responsible for the elevation of liver enzymes will be discontinued, if possible
- Information on potential exposure to environmental chemical agents, alcohol use, and special diets, including adherence to a galactose-restricted diet, will be collected and any factor potentially responsible for the elevation of liver enzymes will be addressed, if possible
- If the patient is asymptomatic and the ALT/AST elevation is not associated with abnormal liver function (e.g. increased bilirubin or abnormal coagulation parameters), the STUDY TREATMENT WILL BE CONTINUED UNDER STRICT MONITORING as below.
- Liver function tests (LFTs) will be monitored every two weeks x2 and then monthly for six months. If ALT or AST decrease to below 3x ULN, then monthly monitoring will continue until resolution. If ALT or AST increase to >5x ULN or if Total Bilirubin increases to >2x ULN, implement the below procedures.
- For ALT or AST >3x ULN lasting six months, perform a hepatic ultrasound and consult with a hepatologist

2. If ALT or AST > 5x ULN OR if ALT or AST >3x ULN and Total Bilirbuin >2x ULN, a retest must be performed within 24 hours

2a. If confirmed ALT or AST > 5x ULN OR if ALT or AST >3x ULN and Total Bilirbuin >2x ULN:

- The event must be reported to the Sponsor within 24 hours.
- STUDY TREATMENT WILL BE DISCONTINUED.
- The following laboratory tests will be performed: alkaline phosphatase, total and conjugated bilirubin, prothrombin time, international normalized ratio (INR), CPK,

serum creatinine, complete blood count, hepatitis A virus (HAV), hepatitis B virus (HBV), hepatitis C virus (HCV), hepatitis D virus (HDV) and hepatitis E virus (HEV)

- A 2 mL serum sample will be collected and stored frozen for future analysis
- An hepatobiliary ultrasonography will be performed.
- All necessary investigations will be performed to rule out autoimmune or alcoholic hepatitis; non-alcoholic steatohepatitis (NASH); biliary tract disease, and hypoxic/ischemic hepatopathy (possibly due to right heart failure or other cardiovascular disease)
- Recent medical history will be investigated specifically for malaise with or without loss of consciousness, dizziness, hypotension, episodes of arrhythmia, and muscular injury.
- Concomitant medications, including recreational drugs, nonprescription medications and herbal and dietary supplement preparations, will be reviewed
- Information on potential exposure to environmental chemical agents, alcohol use, and special diets, including adherence to a galactose-restricted diet, will be collected
- A consult with an hepatologist will be requested.
- Liver Function tests (LFTs) will continue to be monitored every 48 hours until stabilization and symptoms remission (if any), then every 2 weeks until normalization.

2b. If ALT or AST $> 5x$ ULN OR if ALT or AST $> 3x$ ULN and Total Bilirbuin $> 2x$ ULN not confirmed and ALT or AST is $< 5x$ ULN and $> 3x$ ULN (with Total Bilirbuin $< 2x$ ULN) all the procedures listed above under section 1 will be implemented.

2c. ALT or AST $< 3x$ ULN but $> 1.5x$ ULN:

- The event must be reported to the Sponsor within 24 hours.
- LFTs will continue to be monitored every month until normalization or further elevation. If ALT or AST $> 3 x$ ULN, all the procedure above in section 1 will be implemented. If ALT/AST $> 5x$ ULN, OR if ALT or AST $> 3x$ ULN and Total Bilirbuin $> 2x$ ULN, all the procedures listed above under section 2 will be implemented.

APPENDIX H. GUIDANCE IN CASE OF WORSENING RENAL FUNCTION

Renal function must be closely monitored during the study, particularly during administration of potentially nephrotoxic drugs, such as acetaminophen, non-steroidal anti-inflammatory drugs (NSAIDs), fluoxetine, antihistamines, antimicrobials, benzodiazepines, proton pump inhibitors, phenytoin, trimethoprim, fenofibrate, cimetidine, cephalosporins, probenecid, aminoglycoside, amphotericin, ketoconazole, and clofibrate

Urine protein-to-creatinine ratio (UPCR), urine albumin-to- creatinine ratio (UACR) and eGFR will be assessed at each visit. In case of increased UPCR (≥ 200 mg/g), increased UACR (≥ 30 mg/g), eGFR < 30 mL/min/1.73 m², or decreased eGFR $> 30\%$ compared to baseline, a retest must be performed within 24 hours and if the abnormal laboratory result is confirmed, the following actions will be taken:

- The event must be reported to the Sponsor within 24 hours
- Concomitant medications will be reviewed and any potentially nephrotoxic drug must be discontinued
- Recent medical history will be investigated specifically for significant increase or decrease of blood pressure, plasma volume depletion, flu-like symptoms, urinary tract infection, and abdominal pain suggestive of obstructive uropathy.
- If there is no suspected concomitant medication , or if no improvement of renal function is observed after 72 hours of discontinuation of the potentially nephrotoxic drug, and if there is nothing in recent medical history that is likely to cause the abnormal renal function, the study drug will be temporarily discontinued.
- The following urinary markers of kidney injury must be measured: Clusterin (CLU), Cystatin-C (CysC), Kidney Injury Molecule-1 (KIM-1), N-acetyl-beta-D-glucosaminidase (NAG), Neutrophil gelatinase-associated lipocalin (NGAL), and Osteopontin (OPN)
- A renal ultrasound will be performed.
- A nephrologist will be consulted
- Renal function (eGFR, UPCR and UACR) will continue to be monitored every 48 hours until stabilization, then every 2 weeks until normalization.
- At this time, the Investigator in consultation with the nephrologist will decide if the study drug may resume

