The SRC will make recommendations to the Sponsor regarding dose escalation or de-escalation for each cohort based on the results from the previous cohort as described in [Section 3.4](#). The Sponsor will act upon this recommendation and inform the Investigator(s) and the IRB(s)/IEC(s).

The SRC will pay particular attention to DLTs defined as any AT-007-related AE or clinically relevant finding on laboratory tests, ECGs, vital signs, or physical examinations that, in the opinion of the Investigator and/or the SRC, precludes administering the dose to any subject and/or continuing to administer daily doses to the subject who experienced the event. Specific individual subject-level dose stopping criteria for hepatic and renal toxicity are described in [Appendix G](#) and [Appendix H](#). For DLTs, as well as fatal serious adverse events (SAEs) and life-threatening SAEs, breaking the blind will be considered and initiated (as needed) per SRC discussion and agreement.

Dose-escalation will be stopped and de-escalation initiated if:

- ≥ 2 subjects on AT-007 (B and C cohorts of the same dose level considered together) experience a DLT at any time through 24 hours after the last dose of study treatment
- Any subject on AT-007 has a fatal SAE or life-threatening SAE requiring urgent intervention at any time through 24 hours of the last dose of study treatment

The maximum tolerated dose (MTD) will be the dose level below the dose level at which one or more of the events listed above occurs.

Dose escalation within each part of the study will continue until the MTD is identified per the rules described earlier in this section or the SRC and/or Sponsor decide to stop dose escalation. Dose de-escalation, if initiated within any part of the study, will continue until the MTD is identified or the SRC and/or Sponsor decide to stop.

If the events outlined in the above MTD definition do not occur at any dose level in a study part, then the MTD will be the highest dose level in that study part.

If the events outlined in the above MTD definition occur at any given dose level, the Sponsor may decide to investigate a dose higher than the previously well-tolerated dose but lower than the dose at which one of the events outlined in the above MTD definition occurred.

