6.4.1. Day 1 (Study Drug Dosing Day)

Subjects will remain in the CRU on Day 1.

The following procedures will be done before study drug administration on Day 1:

- Measure predose vital signs
- Conduct predose 12-lead ECG
- Collect predose blood sample for PK
- For Cohorts A4 and A5 only, collect predose urine sample for PK
- Randomly assign the subject to either AT-007 or placebo (Note: Unblinded CRU pharmacist will have the randomization schedule.)

Then, study drug (AT-007 or placebo) will be administered to the subject, and the following procedures will be done on Day 1 after the dose:

- For Cohorts A4 and A5 only, collect postdose urine for PK
- Collect postdose blood samples for PK
- Conduct postdose 12-lead ECG
- Measure postdose vital signs
- Feed the subject (3 meals with breakfast provided at ≥ 2 hours postdose)

Note: Blood/urine collection for PK will continue into Day 2.

AE and concomitant medication data will be collected both before and after dose administration on Day 1.

6.4.2. Days 2 and 3

Subjects will remain in the CRU on Day 2. Subjects in Cohorts A4 and A5 only will also remain in the CRU on Day 3.

The following procedures will be done:

- Measure vital signs on both days
- Collect AE and concomitant medication data on both days
- Collect postdose blood sample(s) for PK on both days
- For Cohorts A4 and A5 only, collect postdose urine for PK on both days (Note: Urine collection for PK will continue into Day 4.)
- Feed the subject (3 meals on Day 2)
- Additional Day 3 Procedures
 - Perform physical examination including weight
 - Conduct 12-lead ECG
 - Collect fasting blood sample(s) for clinical laboratory testing (hematology, coagulation and biochemistry)
 - Collect fasting urine sample for urinalysis and, for female subjects of childbearing potential only, urine pregnancy test
 - Schedule the EOS Visit for Day 28 (± 2 days)
 - Discharge subject from the CRU (Cohorts A1, A2, and A3 only) and remind subject/caregiver to fast overnight for at least 10 hours on the day before the EOS Visit and return to the CRU for the EOS Visit before breaking the fast
 - Feed the subject (3 meals) (Cohorts A4 and A5 only)

6.4.3. Day 4

Day 4 procedures apply only to Cohorts A4 and A5.

The following procedures will be done on Day 4:

- Finish the urine collection for PK
- Collect AE and concomitant medications data
- Schedule the EOS Visit for Day 28 (± 2 days)

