7.1.2. Clinical Laboratory Tests

Blood and urine samples for routine clinical laboratory tests will be collected at the visits as indicated in the Schedules of Assessments for Parts A, B, C, D, E, and D Extension ([Appendix A](#), [Appendix B](#), [Appendix C](#), [Appendix D](#), [Appendix E](#), and [Appendix F](#), respectively).

A Clinical Laboratory Improvement Amendments (CLIA) certified laboratory will perform the following clinical laboratory tests:

- Hematology: hemoglobin, hematocrit, total and differential leukocyte count, RBC, and platelet count
- Serum Chemistry: albumin, blood urea nitrogen (BUN), creatinine, total bilirubin, alkaline phosphatase (ALP), aspartate transaminase (AST), alanine transaminase (ALT), sodium (Na⁺), potassium (K⁺), chloride (Cl⁻), lactate dehydrogenase (LDH), calcium (Ca), uric acid, glucose, direct bilirubin (DB), and gamma-glutamyl transferase (GGT)
- Coagulation: prothrombin time (PT) and international normalized ratio (INR)
- Serology: blood tests for hepatitis B surface antigen, hepatitis C antibody, and HIV
- Urinalysis by an automated or manual urine “dipstick” method: pH, specific gravity, protein, glucose, ketones, bilirubin, blood, nitrite, leukocyte esterase, and urobilinogen. If protein, occult blood, nitrite, or leukocyte esterase values are out of range, a microscopic examination will be performed.
- Urine Drug Screen: drugs of abuse (amphetamines, benzodiazepines, barbiturates, cannabinoids, cocaine, opiates)
- Urinary markers of renal function: UACR and UPCR
- Urine cotinine screen (subjects in Parts A, B, and C only)

- Pregnancy test (all female subjects of childbearing potential)
- FSH (for female subjects claiming postmenopausal status)

For Parts D, E, and D Extension only, the following tests will be done in addition to the ones listed above:

- GALT (Part D and Part D Extension but only done once for subjects participating in both Parts) or GALK (Part E) activity in red blood cells
- GALT (Part D and Part D Extension but only done once for subjects participating in both Parts) or GALK (Part E) gene analysis
- Aldose Reductase activity (only done once for subjects participating in both Parts D and D Extension)

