

**APPENDIX A. SCHEDULE OF ASSESSMENTS FOR PART A (SAD IN
HEALTHY SUBJECTS)**

Schedule of Assessments for SAD in Healthy Subjects (Part A)

PROCEDURE	Screening (Days -28 to -1)	Day -1 ^a (Check-in)	Day 1	Day 2	Day 3 ^a (Check-out)	Day 4 ^a (Check-out)	EOS Visit ^b (Day 28±2)
Check-in		X ^a					
Discharge					X ^a	X ^a	
Informed consent	X						
I/E criteria	X	X					
Medical history/updates	X	X					X
Demographic data	X						
Physical examination ^c	X	X			X		X
Vital signs ^d	X	X	X	X	X		X
Electrocardiogram ^e	X	X	X		X		X
Clinical laboratory testing (biochemistry, hematology, coagulation, urinalysis, UACR, UPCR) ^f	X	X			X		X
HIV and hepatitis B & C testing	X						
Urine drug/cotinine screen	X	X					
Pregnancy test (female subjects) ^g	X	X			X		X
Drug administration			X				
Blood sample collection for PK analysis ^h			X	X	X		
Urine collection for PK analysis ⁱ (Cohorts A4 and A5 only) ^j			X	X	X	X	
Adverse Events							Throughout Study
Prior/Concomitant medications	X						Throughout Study

EOS = end-of-study; FSH = follicle-stimulating hormone; HIV = human immunodeficiency virus; I/E = inclusion/exclusion; PK = pharmacokinetic;

SAD = single ascending dose; UACR – urinary albumin to creatinine ratio; UPCR = urinary protein to creatinine ratio

a: Check-in will occur around 11 am on Day -1. For Cohorts A1, A2, and A3, discharge from the clinic will occur on Day 3 after all Day 3 procedures are done and blood samples for PK are collected through 48 hours after the dose. For Cohorts A4 and A5, discharge from the clinic will occur on Day 4 after urine for PK is collected through 72 hours after the dose.

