Clinical laboratory testing (biochemistry, hematology, coagulation, urinalysis) ^f	X	X				X				X
HIV and hepatitis B & C testing	X									
Urine drug/cotinine screen	X	X								
Pregnancy test (female subjects) ^g	X	X				X				X
Drug administration ^h			X	X	X	X	X			
Blood sample collection for PK analysis ⁱ			X	X				X	X	
Adverse events									Throughout Study	
Prior/Concomitant medications	X								Throughout Study	

CSF = cerebrospinal fluid; EOS = end-of-study; FSH = follicle-stimulating hormone; HIV = human immunodeficiency virus; I/E = inclusion/exclusion; MAD = multiple ascending dose; PK = pharmacokinetic; QD = once daily.

a: Check-in will occur around 11 am on Day -1 and Discharge will occur on Day 9 after the blood sample for PK is collected at 48 hours after the Day 7 dose and all Day 9 procedures are done.

b: The EOS visit will be scheduled for 28 (±2) days after the last dose of study drug.

c: All physical examinations will include weight; however, height will be measured only at screening.

- d: Vital signs will be measured at Screening, check-in on Days -1 and 6, predose (within 60 min before the dose) on Days 1 and 7, at 4 hours (± 10 minutes) after the dose on Days 1 and 7, once daily on Days 2, 8, and 9, and at the EOS visit.
- e: Electrocardiograms will be performed at Screening, Day -1 check-in, predose (within 60 min before the dose) on Days 1 and 7, at 2 hours (± 10 minutes) after the dose on Days 1 and 7, and at the EOS visit.
- f: Samples for clinical safety laboratory tests will be collected under fasting conditions.
- g: Serum pregnancy tests at Screening, Day -1, and EOS visits; urine pregnancy tests at other time points. Also, female subjects claiming postmenopausal status will have that status verified with an FSH test at Screening. Once a female subject is verified as postmenopausal or otherwise not of childbearing potential, the subject is exempt for further pregnancy tests. On Day 6, the urine pregnancy test must be done (and the result negative) before study drug is administered.
- h: All doses of study drug will be administered at the clinic.

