- a: Subjects will arrive at the CRU in the morning on Day -1 (approximately 24 hours before the planned first dose). For the Days 12, 20, and 32 check-ins/visits, the subject should arrive after an overnight fast of at least 10 hours (and before breaking the fast) and before taking study drug. On Days 6 and 60, the subject should not have any study drug in his/her possession and should arrive (in a fasted condition) in the morning (before the planned time of study drug dosing to be given in the clinic on Day 6 [no study drug dosing on Day 60]).
- b: Discharge from the 1st, 2nd, and 3rd (last) in-clinic periods of the required portions of Part D will occur on Days 3 (Cohorts D1 and D2) or 4 (Cohort D3), 13, and 34, respectively, after all procedures for that day are done and the last blood sample or urine collection for that in-clinic period is collected.
- c: The EOS visit will be scheduled for 28 (±2) days after the last dose of study drug in the MAD portion.
- d: All physical examinations will include weight; however, height will be measured only at screening.
- e: Vital signs will be measured at Screening, every check-in, every check-out, predose (within 60 min before the dose) and 4 hours (±10 minutes) after the dose on Days 1, 6, 12, 20, and 32; once daily on all other in-clinic days; and at the EOS visit.
- f: Electrocardiograms will be performed at Screening, Day -1 check-in, predose (within 60 min before the dose) and 2 hours (±10 minutes) after the dose on Days 1, 6, 12, 20, and 32 and at the EOS visit.
- g: Samples for clinical safety laboratory tests (hematology, chemistry, coagulation, and urinalysis) will be collected under fasting conditions.
- h: Serum pregnancy tests at Screening, Day -1, and EOS visits; urine pregnancy tests at other time points. Also, female subjects claiming postmenopausal status will have that status verified with an FSH test at Screening. Once a female subject is verified as postmenopausal or otherwise not of childbearing potential, the subject is exempt for further pregnancy tests. On Days 6, 12, 20, and 32, the urine pregnancy test must be done (and the result negative) before study drug is administered.

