- p: Urine for galactitol measurement will be collected over the 24 hours immediately before and the 24 hours immediately after the dose on Day 1. Urine for galactitol measurement will be collected over the 24 hours immediately after the dose on Days 12 and 32 during the MAD period. For each 24-hour collection of urine for galactitol measurement, an aliquot of the total urine collected will be analyzed for creatinine. Also, a spot collection for urine galactitol measurement will be taken at screening.
- q: Visit window \pm 1 day of scheduled visit for all visits except the EOS visit which has a window of \pm 2 days.
- r: These assessments must be performed on Day -1 even if they were already performed earlier during the screening period.

**APPENDIX E. SCHEDULE OF ASSESSMENTS FOR PART E (SAD AND
MAD IN SUBJECTS WITH GALK-DEFICIENT
GALACTOSEMIA)**

Schedule of Assessments for SAD and MAD in Subjects with GALK-deficient Galactosemia (PART E)^o

PROCEDURE	Screening (Days -40 to -1 ^a)	Day 1	Day 2	Day 3 ^b	Day 5	Day 6 ^a	Day 12 ^a	Day 13 ^b	Day 20 ^a	Day 32 ^a	Day 33	Day 34 ^b	Day 60 (±2)	EOS Visit ^c Day 60 (±2)
Check-in	X ^a (Day -1)						X ^a			X ^a				
Discharge				X ^b				X ^b					X ^b	
Informed consent	X													
I/E criteria	X ^p													
Medical history/updates	X ^p													X
Demographic data	X													
Physical examination ^d	X ^p					X	X		X	X			X	X
Vital signs ^e	X ^p	X	X	X		X	X	X	X	X	X	X	X	X
Electrocardiogram ^f	X ^p	X				X	X		X	X				X
Clinical laboratory testing ^g	X ^p					X	X		X	X				X
GALK activity in red blood cells and GALK gene analysis	X													
Aldose Reductase activity	X													
HIV and hepatitis B & C testing	X													
Urine drug screen	X ^p													
Pregnancy test (female subjects) ^h	X ^p					X	X		X	X				X
Drug administration ^j		X												
5-day washout ^k				X										
Blood sample collection for PK analysis ^l		X	X	X			X	X		X	X	X		
Blood sample collection ^m for galactose, galactitol, galactose-1-p and other galactose metabolites	X ^p	X	X	X			X	X		X	X	X		

PROCEDURE	Screening (Days -40 to -1 ^a)	Day 1	Day 2	Day 3 ^b	Day 5	Day 6 ^a	Day 12 ^a	Day 13 ^b	Day 20 ^a	Day 32 ^a	Day 33	Day 34 ^b	Day 60 (±2)	EOS Visit ^c
Urine sample collection ⁿ for galactitol	X ^p	X	X				X	X		X	X			
Adverse events														Throughout Study
Prior/Concomitant medications	X ^p													Throughout Study

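### The renal stopping guidance needs UPCR and UACR at each visit, but the Part B, C, D and E schedules and on-treatment visit lists name only dipstick urinalysis

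*Protocol*

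**What the plan says.** Appendix H of the protocol sets the monitoring rule for UPCR, UACR and eGFR in a sentence that ends "UACR) and eGFR will be assessed at each visit". It has four triggers: UPCR ≥200 mg/g, UACR ≥30 mg/g, eGFR <30 mL/min/1.73 m², and a fall in eGFR of more than 30% from baseline. A trigger calls for a retest within 24 hours. If confirmed, it leads to a Sponsor report, a medication review and, under stated conditions, temporary interruption of study drug. Section 3.5 gives this appendix its force: "Specific individual subject-level dose stopping criteria for hepatic and renal toxicity are described in" Appendices G and H.

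Section 7.1.2 defines urinalysis as a dipstick method, with microscopy if certain values are out of range. It lists the ratios as a separate item for all parts, "Urinary markers of renal function: UACR and UPCR", and refers to the schedules for timing.

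The schedules differ by part:

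- Appendix A (Part A) has a row reading "Clinical laboratory testing (biochemistry, hematology, coagulation, urinalysis, UACR, UPCR".
- Appendices B and C have a row that stops at "Clinical laboratory testing (biochemistry, hematology, coagulation, urinalysis".
- Appendices D and E define the panel in footnote g: "Samples for clinical safety laboratory tests (hematology, chemistry, coagulation, and urinalysis) will be collected under fasting conditions".
- Appendix F (Part D Extension), footnote j, names both ratios.

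The visit lists follow the same pattern. Section 6.5.4 (Part B Day 6, adopted for Part C by Section 6.6) and Section 6.7.3 (Parts D and E Day 6) say "Collect fasting urine sample for urinalysis and, for female subjects of childbearing potential only, urine pregnancy test". Days 12, 20 and 32 in Sections 6.7.4, 6.7.6 and 6.7.7 also name urinalysis alone. Sections 6.8.3 and 6.8.4 name both ratios on Days 30, 60 and 90 of the Extension. Outside dosing, Sections 6.2 (screening), 6.3 (Day -1) and 6.9 (end of study, EOS) name both ratios for all parts.

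SAP Sections 3.2.2 and 7.12.3 mention none of UPCR, UACR or eGFR.

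**The concern.** Safety is the primary endpoint, and Appendix H is the subject-level renal rule. A rule can act only on results that the schedule produces. Two of its four triggers are in mg/g, which a dipstick cannot supply. Abnormal dipstick protein prompts microscopy under Section 7.1.2, not a ratio.

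The sponsor gives these cut-offs weight elsewhere. Section 4.2.2, exclusion criterion 4, uses the same UPCR and UACR limits for Part D entry, subject to Investigator discretion, and Section 4.3.2 carries them to Part E. A subject could be screened on these markers and then take all 28 doses with no scheduled recheck on treatment. What is at stake is detection of protein or albumin leak during dosing; filtration is covered separately by serum creatinine.

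**Working it through.** The plan states no figure to reproduce. The check is a count of visits, followed by day arithmetic.

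**Count.** I took the safety-lab visits after Day -1 and before EOS (end of extension for the Extension) and asked whether the visit list or the schedule names UPCR and UACR. This is a lenient reading of each visit, since it ignores visits with no safety labs.

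| Part | On-treatment lab visits | Visit list names ratios | Schedule names ratios |
|---|---|---|---|
| B | Day 6 | 0 of 1 | No |
| C | Day 6 | 0 of 1 | No |
| D | Days 6, 12, 20, 32 | 0 of 4 | No |
| E | Days 6, 12, 20, 32 | 0 of 4 | No |
| D Extension | Days 30, 60, 90 | 3 of 3 | Yes |

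Part A is a partial case: the Day 3 visit list (Section 6.4.2) omits the ratios, but the Appendix A row supplies them. In Parts B to E neither source does.

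**Doses in the interval.** Parts B and C: 7. Parts D and E: 1 + 27 = 28.

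**Shortest interval between scheduled ratio results.** This is for a subject who completes, at a site following the visit lists, with the ratios measured on Day -1. There is no Day 0, so Day -1 to Day 1 is one day.

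- Parts B and C, Day -1 to EOS Day 35: 1 + 34 = 35 days (33 to 37 with the ±2-day EOS window).
- Parts D and E, Day -1 to EOS Day 60: 1 + 59 = 60 days (58 to 62).

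**Longest interval.** Section 6.3 lets UPCR and UACR be skipped on Day -1 if they were done at prescreening or screening within 60 days before Day 1. Screening falls within 28 days of dosing in Parts A to C and within 40 days in Parts D and E, so a result from the screening visit always meets that condition.

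- Parts B and C, Day -28 to Day 35: 28 + 34 = 62 days (60 to 64). No footnote in Appendix B or C overrides the waiver.
- Parts D and E: Appendix D footnote r and Appendix E footnote p say of the lab row, among others, "These assessments must be performed on Day -1 even if they were already performed earlier during the screening period". If that row covers the ratios, the waiver is overridden for them. If the row is limited to the panel in footnote g, it is not, and Day -40 to Day 60 gives 40 + 59 = 99 days (97 to 101).

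**The case against.** The strongest reply is that Appendix H and Section 7.1.2 are themselves operative. A site is bound by the each-visit rule, and Section 7.1.2 puts the ratios among the clinical laboratory tests, so a site could read them into the lab row of any schedule. The Part B to E rows and footnotes also leave the ratios out at screening, Day -1 and EOS, where Section 6 requires them, which suggests incomplete drafting. This stands to the extent that a reader might infer that the ratios were not collected on treatment; the documents do not show that. It does not remove the conflict. Section 7.1.2 defers timing to schedules that spell out the panel without the ratios, while Appendices A and F write them in.

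A reader might also infer fixed gaps of 35 and 60 days. The Section 6.3 waiver prevents that. In Parts D and E there is a further difficulty: footnotes r and p can guarantee a Day -1 ratio only if the lab row includes the ratios, and the same row is marked on Days 6, 12, 20 and 32. The 35 and 60 days are therefore lower figures, conditional on a Day -1 result and on the site following the visit lists.

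Nor is the kidney unmonitored. Serum creatinine and dipstick protein are scheduled, and Section 6.10 allows further tests at unscheduled visits. None of these applies the mg/g thresholds.

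On the SAP, a reader might infer a deliberate decision not to analyse the markers. Version lag is more likely. The SAP says that it follows protocol Version 6.0, its own screening list lacks the ratios, and its Extension size (16 against 28) and screening window (40 against 60 days) differ from this protocol. It plans subject-level laboratory listings and summarises serum chemistry, which includes creatinine. A count of subjects meeting each trigger is a reporting preference that the plan never promised.

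**Conclusion.** The concern holds as an internal inconsistency that should be corrected. Appendix H requires both ratios at each visit; the Part B to E schedules and dosing-period visit lists do not name them at any on-treatment lab visit. For a site working from those lists, the UPCR and UACR triggers could not be applied during dosing, while both eGFR triggers remain workable. Scheduled ratio results would be at least 35 days apart in Parts B and C and 60 in Parts D and E, ±2 days. They could be about 62 days apart in B and C and, on the narrow reading of footnotes r and p, about 99 in D and E.

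These intervals assume a completing subject and no additional testing under Appendix H or at unscheduled visits. The documents do not show what sites actually collected. The SAP omission is secondary.

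**What to change.** Add UPCR and UACR to the lab rows and footnotes of Appendices B to E and to the on-treatment visit lists in Sections 6.5 to 6.7, for any cohort not yet dosed. Fasting urine is already collected at these visits, so the cost is a modest assay charge. Completed cohorts cannot benefit. How many remain open is not clear: the protocol keeps Version 5.0 wording on pending cohorts, Section 5.3 describes the Part D and E drug supply in the past tense, and SAP Section 4 plans database lock after Part D.

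Secondarily, bring the SAP up to the current protocol. Sections 3.2.2 and 7.12.3 should summarise UPCR, UACR and derived eGFR (observed values and change from baseline) wherever collected, including the Part D Extension. This is useful whichever cohorts are open and costs a little extra tabulation. A count of subjects meeting each Appendix H trigger is optional.
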